#### 9.2.3 Follow-up Assessments

Follow-up visit time-points specified in the INTERMACS® protocol include: At discharge, 1 week, 1 month, 3 months, 6 months and every 6 months until outcome/ 2.5 years.

At discharge assessments recorded in the INTERMACS® database include: adverse events and discharge date.

Assessments at one week and one month include: hemodynamics, laboratory values, medications, echocardiogram, medical condition as described by NYHA class and adverse events.

Assessments at 3 and 6 months, and then every 6 months until outcome / 2.5 years include: laboratory values, medications, hemodynamics, echocardiogram, medical condition as described by NYHA class and INTERMACS® patient status, neurocognitive testing, quality of life testing, exercise function and adverse events.

Every attempt should be made to perform evaluations at the designated time points. Visits and associated visit windows will be as per the INTERMACS protocol and procedures. While per the INTERMACS protocol, the Month 6 visit has a  $\pm 60$  day window, it is recommended that the Primary Endpoint visit occur at Month 6 + 60 days, whenever possible.

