## Designated Interval Follow-up

A major feature of the database design is the provision of information both by event and by designated time interval. In this way, the crucial events are submitted in real time, but there are also regularly scheduled checkpoints at which any important events during follow-up intervals will be captured. The first routine post-operative follow-up will be at 1 week. The remaining interval follow-up visits occur at 1 month, 3 months, 6 months, and every 6 months for the life of the device. If the device is explanted without transplantation, the patient will be followed for 1 year following explant for the major events of death or transplantation.

The follow-up forms will all include information on vital signs and volume status, medications, basic laboratory values, and device settings. New York Heart Association (NYHA) functional status will be noted. At each time interval beginning with the 3-month follow-up, re-assessment will be documented regarding current intent as bridge to recovery, transplant, likelihood of eligibility for transplant, or permanent support, with a checklist of considerations relevant to that decision. Echocardiographic information will be included regarding function of both ventricles and atrioventricular valves. Hemodynamic measurement regarding filling pressures, pulmonary pressures, and cardiac output will be included when available.

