## Adverse Events

Data on specific adverse events will be collected by two mechanisms:

- (1) The occurrence of **hemolysis**, **hypertension** and **right heart failure** are considered 'triggered events'. These events are 'triggered' based on the relevant medical data collected at follow-up and re-hospitalization.
- (2) Other adverse events (see MOP Appendix A for a complete list) will be identified and collected through routine data acquisition at the specified follow-up intervals or at time of event.

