2.4.3. Other Endpoints

Additional endpoints in this study include:

1. Success at 6 months defined as alive on original device or transplanted or explanted for recovery by month 6.
2. Overall Survival on HVAD (Time to Death on original device).

3. Frequency and rates of adverse events per INTERMACS® definition throughout original VAD support.
4. Time on Cardiac Pulmonary Bypass.
5. Perioperative Bleeding and Transfusions (within 48 hours post-op).
6. Length of initial ICU stay.
7. Prevalence and causes of re-hospitalizations (within 6 month period following implantation).
8. Health Status improvement at 6 month, as measured by KCCQ and EuroQol EQ-5D.
9. Functional status improvement, as measured by NYHA and 6-minute walk.
10. Success at 6 months (defined like the primary endpoint) for those screen failures who undergo thoracotomy.

Additional endpoints include observed and change in laboratory, hemodynamics and echocardiogram parameters and neurocognitive testing scores at 6 months. Additional observational endpoints will also be assessed at 6 months. The additional endpoints will be analyzed descriptively, i.e., no inferential analysis will be performed and conclusions will be formulated with caution as these endpoints are not powered.

Time-to-event outcomes will be presented using Kaplan-Meier curves. Quantitative outcomes will be summarized and the corresponding 95% confidence intervals will be derived.

Categorical outcomes will be summarized by presenting frequency and percentage results as well as the corresponding 95% confidence intervals. In particular, adverse events and stroke events summaries will be presented by calculating prevalence (frequency) and event rates (events per patient-year).

Strokes are neurological events specified as an ICVA or an HCVA, as per the current INTERMACS event definition (See Appendix D of the protocol).

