2.5. Long-Term Follow-up Analyses

Adverse events through data cut will be included in the initial study results report. No other long term analysis will be included at that time. All data will be included in the final report.

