1. Calculate the patient-years contributed by each subject. The time in the study starts at enrollment. The end date would be the last follow-up date (end of study), unless the subject has an explant (when the pump is removed, turned off, or exchanged), dies, or is lost to follow-up prior to the end of study. The patient years are calculated as (date of explant or death or last follow-up or end of study – date of enrollment + 1)/365.24. When the number of days is negative, the value will be missing for the patient-years.
2. Sum the patient-years across all subjects in the study. This is the denominator.
3. Sum the total number of events for a particular adverse event (prior to exchange). If a subject has patient-years that is missing, the AEs will not be counted for these subjects (e.g., subjects who have ongoing AEs that are entered into the database, an exchange after the AE but prior to enrollment).
4. The adverse event rate per patient-year = (Sum of the total number of events for the particular adverse event (prior to exchange))/(Sum of the patient-years across all subjects in the study).

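### For subjects still on the original device, the SAP's adverse event rate has no common end date for events and patient-years, so the initial report's descriptive rates can be biased upward by a conditional amount

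*SAP*

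**What the plan says.** SAP 3.2, item 2, builds the rate in four steps. Step 1 sets each subject's exposure: "The time in the study starts at enrollment", and "The end date would be the last follow-up date (end of study), unless the subject has an explant" (removal, switching off or exchange of the pump), dies or is lost to follow-up. Step 3 sets the numerator: "Sum the total number of events for a particular adverse event (prior to exchange", with no other upper date. Step 4 divides one by the other and repeats the same limit.

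SAP 2.4.3 gives the scope as "Frequency and rates of adverse events per INTERMACS® definition throughout original VAD support", so the rates are not confined to six months. SAP 2.5 adds: "Adverse events through data cut will be included in the initial study results report". The data cut does not appear in the rate formula.

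Protocol 9.2.3 sets visits "At discharge, 1 week, 1 month, 3 months, 6 months and every 6 months until outcome/ 2.5 years". In Protocol Appendix A, A.4.3, Designated Interval Follow-up says that "the crucial events are submitted in real time". The Adverse Events paragraph of the same section says that events other than the triggered ones "will be identified and collected through routine data acquisition at the specified follow-up intervals or at time of event".

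**The concern.** A rate per patient-year is interpretable only if events and time at risk cover the same period. For a subject on support at the initial report, the data cut bounds the events, while the last follow-up bounds the time. After Month 6 these dates can be up to six months apart, and the registry allows events to be entered in between.

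The bracketed mention of end of study does not close the gap. Protocol 6.2.2 defines end of study as the last visit of the last subject, which has not happened when the initial report is written. Nothing in the SAP equates the last follow-up with the data cut.

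A smaller mismatch of the same kind: step 1 stops time when the pump is removed or turned off, but steps 3 and 4 stop events only at exchange. The scope in SAP 2.4.3 limits this, but the formula does not say so.

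At stake is a planned safety output, on the same scale as the earlier HVAD rates in Protocol 4.2.1 and 4.2.2. A rate that depends on where the cut falls between visits could also differ between initial and final reports for a computational reason.

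**Working it through.** **No stated figure to reproduce.** The documents give no event rate or cut date for this trial. Events divided by patient-years does reproduce the earlier-study tables: 14/22.3 = 0.63 (Protocol 4.2.1, bleeding, 0-180 days) and 101/252.6 = 0.40 (Protocol 4.2.2, bleeding).

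**One record.** Last visit Day 365, infection entered Day 500, still on support at a Day 520 cut. The literal rule gives 1 event in 365/365.24 = 1.00 patient-years. Time to the cut is 520/365.24 = 1.42.

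**Inputs from the documents**
- 145 subjects.
- First implant Q4 2014 and last implant Q1 2016 (Protocol 6.2), hence roughly 12-18 months of accrual.
- Visit times from Protocol 9.2.3.

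**Assumed inputs**
- Uniform accrual.
- Data cut 6-9 months after the last implant.
- Exponential exit from the original device at h per year. In ADVANCE, 88/140 were alive on the original device at Day 180 (Protocol 4.2.3), so h = -ln(88/140)/0.5 = 0.93. Values of 0.6 and 0.4 are taken as a range. In the international study, 38 of 50 entering the second period imply about 0.56.
- f, the share of events after the last follow-up that are already entered at the cut.

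**Formula.** A subject implanted C years before the cut has expected time on device to the cut of (1 - e^(-hC))/h. With V(C) the last scheduled visit at or before the cut, the time that the literal rule omits is (C - V(C))e^(-hC). Let D and G be the totals of these two quantities over 145 subjects. For a constant event rate, inflation = f x G/(D - G).

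**Last follow-up read as last scheduled visit, f = 1, 18-month accrual**

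| Cut after last implant | h per year | Patient-years to cut, D | By the literal rule, D - G | Inflation |
|---|---|---|---|---|
| 6 months | 0.93 | 103.1 | 91.8 | 12.3% |
| 6 months | 0.6 | 123.6 | 106.8 | 15.7% |
| 6 months | 0.4 | 139.3 | 117.8 | 18.3% |
| 9 months | 0.93 | 114.1 | 104.0 | 9.7% |
| 9 months | 0.6 | 140.1 | 124.4 | 12.6% |
| 9 months | 0.4 | 160.6 | 140.0 | 14.7% |

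This is the range of about 10-18%.

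**Other assumptions**
- *No exits, 12-month accrual, cut at 6 months.* Time to the cut runs evenly from 6 to 18 months (mean 12). The last visit is Month 6 for half and Month 12 for half (mean 9). 12/9 = 1.33, so 33%.
- *Half of later events entered (f = 0.5).* 12.3% becomes about 6.2%. *None entered (f = 0):* 0%.
- *Last follow-up read as last contact*, mean gap 0.5-1 month, 15-month accrual, cut at 6 months: 2.3% (0.5 month, h = 0.93) to 8.0% (1 month, no exits), or about 2-8%.
- *Falling event rate.* Protocol 4.2.1 shows bleeding at 0.63, 0.22 and 0.08 per year in successive periods. On the 18-month grid, with the benchmark closing both events and time at the last visit, the excess is about 3-6%.

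**The obvious repair.** If exposure ran to the cut, a visit-captured event would gain time without a matching chance of being counted. On the same grid its rate would fall by between 1 - 104.0/114.1 = 9% and 1 - 117.8/139.3 = 15%.

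**The case against.** The strongest reply is that the text does not fix the reading on which the bias depends. The SAP never says that the last follow-up is the last scheduled visit. It could be last contact, or the bracket could be stretched to mean the cut. SAP 2.5 says which events enter the report; it does not define the rate's numerator. This stands in part. It makes the size uncertain, but an undefined end date that lets two programmers get different rates from the same data is itself the defect.

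A reader might infer that every category's rate will come out 10-18% too high under the plan's own schedule. The documents do not support that. They supply accrual quarters and visit times only; the cut date, exit rate and completeness of entry between visits are assumptions. Nor is the effect uniform. Hemolysis, hypertension and right heart failure are derived from follow-up and re-hospitalization data (Protocol Appendix A, A.4.3, and Appendix D, Triggered Adverse Events), so they are little affected. Real-time entry is promised only for crucial events.

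The net direction of the reported rates is not established either. Starting the clock at enrollment adds time before implant. If enrollment precedes implant by 7-14 days (assumed), rates fall by about 3-6% with h = 0.93, 15-month accrual and a 6-month cut. That is a separate feature of step 1, so the claim here concerns this mismatch taken alone.

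Finally, these rates are one of ten other endpoints, are descriptive (SAP 2.4.3) and carry no inference (SAP 2.4.7). Counts and percentages of subjects are reported alongside and do not use the denominator. All of this stands and limits the importance.

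**Conclusion.** The point holds as a missing common cut-off. For subjects on the original device at the initial report, the literal rule counts events after the last follow-up without their exposure, which by itself can only raise the rate.

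The size is conditional:
- 0% if later events are captured only at visits.
- About 2-8% if last follow-up means last contact with short gaps.
- About 10-18% if it means the last scheduled visit, all later events are entered, the event rate is constant, accrual takes 18 months, the cut falls 6-9 months after the last implant, and exits run at 0.4-0.93 per year.
- Up to about 33% with no exits.
- About 3-6% for event types whose rate falls with time as bleeding did in the international study.

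The final report is essentially unaffected, because last follow-up and end of study then coincide. The primary and secondary tests do not use these rates.

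**What to change.** In SAP 3.2, item 2, define one end date per subject: the earliest of exchange, explant or pump turned off, transplant, death, withdrawal or loss to follow-up, end of study, and the last completed follow-up on or before the data cut. Define last completed follow-up, and say whether the record of an exit counts as one. Sum patient-years to that end date. In steps 3 and 4, replace the limit at exchange with a limit to events with onset on or before the subject's end date. List later events separately.

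Do not simply run exposure to the data cut, since that would understate the rates of events captured only at visits.

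The cost is a few sentences in the SAP and one date filter in the program, with no new data. The downside is that a few late events leave the rate, though they stay in the listing.

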\*Events that have an onset date of 0-30 days and which reoccur in the same patient past 30 days are counted in both 0-30 day and 31-180 day periods.

CONFIDENTIAL

There were eight subject deaths during the 180-day study period. Six deaths occurred in subjects with their originally implanted device and two deaths occurred after device exchange. There were 26 device malfunctions reported for 20 patients during the study period. Seven (5.0%) were due to the LVAD component; of these 6 involved thrombosis events, necessitating exchange.

The pre-specified primary endpoint analysis was a comparison of success rates using a non-inferiority margin of 15%. In the HVAD group the success rate in the Intent-To-Treat (ITT) / Safety Population at 180 days was 90.7% (127/140) and in the Per Protocol population 92.0% (126/137). The success for both Safety and Per Protocol populations in the Control group was 90.1% (448/497). The Primary analysis found that the 95% one-sided upper confidence limit (UCL) on the difference in success rates between HVAD group and controls was 4.5% for the Safety population and 0.9% for the Per Protocol population. Each of these limits was less than the 15% non-inferiority margin ( $p < 0.0001$ ).

Survival was defined as transplanted, or alive on device support, or alive after device explant for recovery. The overall Kaplan-Meier survival at 180 days in the HVAD group was 93.9% in the Safety population and 94.2% in the Per Protocol population. The corresponding survival for the INTERMACS control group was 90.2%. In addition survival status at Day 180 was assessed for all HeartWare® HVAD patients irrespective of meeting a predefined outcome (transplant or explant). There were 130/140 (92.9%) of patients alive at day 180 (88/140 were alive on the original device, 5/140 were alive post device exchange, and 37/140 were alive post-transplant).

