### 7.2 Subject Participation and Study Duration

All subjects will be followed for the primary endpoint, and at subsequent follow-up visits, according to the approved INTERMACS® protocol and using data from INTERMACS®.

Data collection for analysis and subject status for inclusion in analyses will be assessed as follows:

- Subjects who have been transplanted prior to month 6 post implant will be considered complete at the time of the primary endpoint visit time-point.
- Subjects, who have a device exchange prior to month 6, will be evaluated according to the original implant date.

- Subjects who remain on device support after the primary endpoint time-point, either the original device or exchange device, will be followed according to the INTERMACS® protocol until transplant, or until 2.5 years post implant of the original device. A subject's study participation is considered complete at either the time of at induction of anesthesia for transplant, or at the 2.5 year post implant visit.
- Subjects who have been explanted for recovery prior to month 6 will be followed until their next scheduled follow-up visit according to the INTERMACS® protocol, at which time their participation in the study is considered complete.
- The per-protocol analysis population will include those thoracotomy subjects with the outflow in the ascending aorta only. As a result, enrollment may exceed sample size requirements.
- The per-protocol analysis population will include those thoracotomy subjects with the procedure performed on-pump only. As a result, enrollment may exceed sample size requirements.

Subject data will be evaluated for a maximum of 2.5 years.

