2.4.1. Primary Endpoint

The primary endpoint is success at 6 months for all enrolled and implanted subjects. Success is defined as follows:

- Alive on the originally implanted device at 6 months, and the subject has not had a severe stroke; or
- Transplanted by Month 6, and the subject has not had a severe stroke prior to transplant; or
- Explanted for recovery by Month 6, and the subject has not had a severe stroke prior to explant for recovery.

All subjects with stroke events from implant to Month 6 will be required to remain in study follow-up until the post-stroke mRS measure (≥ 3 months post stroke event) is obtained, even if this occurs at the next expected follow-up visit. If a stroke subject is alive at 6 months, but dies before the post-stroke mRS is obtained, the subject will be considered a failure with regard to the primary endpoint.

A stroke is considered severe if either:

- The first mRS score assessed ≥ 3 months post stroke event is ≥ 4 ; or

- The follow-up (≥ 3 months post stroke event) mRS score is missing and the day-of-event mRS is ≥ 4 .

Specifically, any subject experiencing any of the following events will be considered a failure:

- Death by any cause prior to 183 days post-implant and prior to transplant or explant for recovery
- A severe stroke occurring prior to 183 days post-implant and prior to transplant or explant for recovery
- A stroke followed by death within 91 days post-event occurring prior to 183 days post-implant and prior to transplant or explant for recovery

Subjects with a stroke with no available mRS and no death ≥ 91 days post-stroke occurring prior to 183 days post-implant and prior to transplant or explant for recovery will be considered missing in the primary analysis.

All subjects with at least 182 days of documented follow-up without meeting any of the above failure criteria will be considered a success. Subjects not considered a success or a failure will be excluded from the analysis.

N.B. As INTERMACS only includes visits every 6 months starting at the 6 month visit, it should be noted that should a stroke occur after 3 months, a post-event mRS score may not be obtained until the 12 month visit.

Hypotheses:

$$H_0: \pi_T \leq 77.5\%$$

$$H_a: \pi_T > 77.5\%$$

where π_T = the proportion of the patient population experiencing success for the Thoracotomy group.

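### The SAP's readable survival endpoint and adverse event rates stop at pump exchange, and no analysis is defined for what happens to exchanged subjects afterwards

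*SAP*

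**What the plan says.** **Follow-up.** Protocol 7.2 states: "Subjects who remain on device support after the primary endpoint time-point, either the original device or exchange device, will be followed" until transplant or 2.5 years after the first implant. Protocol 9.2.6 has adverse events collected for as long as the subject takes part.

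**Survival.** The one survival endpoint that can be read in SAP 2.4.3 is "Overall Survival on HVAD (Time to Death on original device").

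**Adverse events.** The endpoint in SAP 2.4.3 is "Frequency and rates of adverse events per INTERMACS® definition throughout original VAD support". For rates, SAP 3.2 item 2 ends a subject's patient-years at the last follow-up date "unless the subject has an explant (when the pump is removed, turned off, or exchanged), dies, or is lost to follow-up". The numerator instruction is "Sum the total number of events for a particular adverse event (prior to exchange").

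**Primary endpoint.** The failure list in SAP 2.4.1 includes "Death by any cause prior to 183 days post-implant and prior to transplant or explant for recovery". Exchange is not among the events that end this count. The severe-stroke rule and the stroke-followed-by-death rule have the same limits.

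**General statements.** SAP 2.4.7 describes a count-and-percentage table of adverse events with no stated exchange cut-off. SAP 2.5 says that adverse events up to the data cut go into the initial report and all data into the final one. SAP 2.5.2 offers later analogues of the endpoints where possible. None of these gives a method for events after exchange. Much of SAP 2.4.7, and the protocol's text on additional endpoints, is redacted.

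**The concern.** The study's objective is the safety and effectiveness of implanting the pump by thoracotomy. A subject whose first pump has been exchanged is still a subject implanted by thoracotomy, and the protocol goes on collecting that subject's deaths and adverse events. Under the readable SAP those data enter no defined survival curve and no defined rate.

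Original-device results answer a legitimate but narrower question: what happens while the first pump is in place. They do not tell a reader how many implanted subjects were alive at 6 months or at the end of follow-up, or what complications followed an exchange.

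There is also a small internal mismatch. Exposure ends at any removal of the pump, but events are cut only at exchange. Read literally, an adverse event after explant for recovery would add to the numerator with no matching patient-time.

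**Working it through.** **1. Which events are counted where**

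| Event | Primary endpoint (SAP 2.4.1) | Survival endpoint (SAP 2.4.3) | AE rate (SAP 3.2) |
|---|---|---|---|
| Death after exchange, before day 183 | Failure | Not counted | n/a |
| Death after exchange, day 183 on | Outside the window* | Not counted | n/a |
| Severe stroke after exchange, before day 183 | Failure | n/a | Not counted |
| Other AE after exchange | Not a component | n/a | Not counted |

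*Except a death that follows a stroke which itself occurred before day 183.

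The primary endpoint cannot stand in for mortality. By definition it requires the first pump still to be in place (or transplant or recovery), so an exchanged subject who lives and one who dies both fail. The operational failure list does not name exchange, which is a separate matter to reconcile. On either reading the result is a composite that ends at 6 months.

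**2. Counts from the earlier US trial (Protocol 4.2.3)**

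- Reproducing the stated figure: alive at day 180 = 88 + 5 + 37 = 130, and 130/140 = 92.9%, as stated.
- Deaths in the 180-day period: 8. The protocol says: "Six deaths occurred in subjects with their originally implanted device and two deaths occurred after device exchange".
- Share of deaths after exchange: 2/8 = 25%. The exact 95% limits are the 2.5% point of Beta(2, 7) and the 97.5% point of Beta(3, 6), giving 3% to 65%.
- Exchanged subjects: at least 5 alive + 2 dead = 7, and 7/140 = 5%. This is a minimum, because anyone exchanged and then transplanted is counted elsewhere.
- Mortality: 2/7 = 28.6% after exchange (exact 95% CI 3.7% to 71%), against 6/133 = 4.5% in everyone else, a group that includes transplanted subjects.

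**3. Scaled to 145 implants**

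- Exchanged: 145 × 7/140 = 7.25, about 7.
- Deaths by 6 months: 145 × 8/140 = 8.3. Of these, 145 × 2/140 = 2.1 come after exchange and 145 × 6/140 = 6.2 on the original device.
- The on-device curve would therefore lack about 2 of 8 deaths.

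**4. Range under stated assumptions**

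The international study (Protocol 4.2.1) had 6 of 50 patients with pump replacement within 180 days (12%) and one more after a year. If that was a different patient, the total is 7/50 = 14%. I assume exchange in 5% to 14% of subjects and mortality after exchange of 5% to 50%.

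- Low: 145 × 0.05 × 0.05 = 0.4 deaths off the on-device curve.
- High: 145 × 0.14 × 0.50 = 10.2 deaths.
- Patient-time after exchange, as an upper bound with everyone followed to 30 months: 7 × (30 − 12)/12 = 10.5 years for 7 exchanges at month 12, and 20 × (30 − 3)/12 = 45 years for 20 exchanges at month 3. The most the study could accrue is 145 × 2.5 = 362.5 patient-years.

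**5. Size of the numerator mismatch**

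It affects only subjects whose pump is removed or turned off without exchange and who then have a recorded adverse event. SAP 2.4.3 already confines the endpoint to original VAD support. The INTERMACS protocol (A.4.3) limits follow-up after explant without transplant to death or transplantation. Few events, if any, would be misplaced.

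**The case against.** The strongest reply is that the important deaths are already counted. That is correct up to day 183. A reader might infer that the SAP stops counting deaths altogether at exchange, or that a technique causing more exchanges would look no worse on mortality or stroke. The documents do not support either inference for the 6-month primary endpoint: any-cause death and severe stroke count there regardless of exchange, so both post-exchange deaths of the earlier trial would have been failures. Pump replacement is also itself a major device malfunction under the INTERMACS definitions, which is a reported adverse event category.

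Three other strong readings also fail:

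- *The on-device curve would show only 6 of 10 deaths.* Ten of 140 were not alive at day 180, but the protocol places only two deaths after exchange. The supported fraction is 6 of 8.
- *Thoracotomy leads to exchanges.* The earlier US trial used sternotomy. Four of its seven pump failures fell in days 31 to 180, and six of the seven involved thrombosis.
- *The later data are omitted outright.* SAP 2.5 promises all data in the final report, and redacted text may say more. What can be said is that no method is defined in the readable text.

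It is also fair that on-device analysis is a defensible choice for an implant technique, since events after exchange reflect a second operation and a second pump. For exchange, numerator and denominator stop together, so the rate is coherent. These endpoints are descriptive. All of this supports keeping the original-device results, but none of it supplies the missing all-cause survival or post-exchange rates.

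**Conclusion.** The point holds as a gap in the descriptive safety analyses, not as an error in the primary test. Three things have no defined analysis: adverse events after exchange, deaths after exchange from day 183 on (the stroke exception aside), and all-cause survival from the original implant.

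The best available estimate is about 7 exchanged subjects among 145, with about 2 of 8 six-month deaths absent from the on-device curve. It rests on two deaths in one sternotomy trial and is very imprecise. The assumed range is 0.4 to 10 deaths.

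The conclusion assumes that the redacted part of SAP 2.4.7 does not already contain these analyses. The mismatch between event and exposure cut-offs is real as written but small. Overall this is an inexpensive improvement worth making.

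**What to change.** - Keep the original-device survival and adverse event results as planned.
- In SAP 2.4.3, add descriptive all-cause survival from the original implant, with exchange not ending follow-up, at 6 months and at the end of follow-up. State how transplant and explant for recovery are handled. The protocol's 2.5 years and the 5 years in SAP 1.2 must be reconciled so that the end of follow-up is defined once.
- Add a second set of adverse event rates over all HVAD support, exchange devices included, with patient-time extended to match.
- In SAP 3.2 item 2, count events that occur on or before the end date used for that subject's patient-years.

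The cost is SAP wording plus one curve and one table. No new data are needed; the earlier US trial reported day-180 survival status regardless of predefined outcome. The reported mortality may look slightly less favourable.
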